The individual can choose not to participate.

Participant Withdrawal from Research/ Research Activities

Research activities are limited to five weeks.

Participants may withdraw from the study at any time and for any reason without prejudice. The withdrawal must be documented.

Monitoring/Reporting of AE/SAE

AEs and SAEs will be detected using the weekly surveys. On a weekly basis, participants are asked if they have stopped taking the product due to side effects. If they answer in the affirmative, they can provide more information on the symptoms and their severity. Participants can also report AEs and SAEs to the study staff at any time via phone or email.

An AE is defined as any reported side effect of the product that is likely due to Veillonella itself. Based on our previous work, we anticipate mild and transient gastrointestinal upset as well as mild anxiety as possible common AEs.

An SAE is defined as any severe and/or unexpected side effect that is life threatening, requires medical or surgical intervention, or is otherwise an important medical event for the patient. SAEs are also AEs that result in hospitalization, disability or permanent damage, or death. These will be reported to the FDA.

FitBiomics is utilizing a company called SafetyCall for AE monitoring and reporting in this study. SafetyCall will provide adverse event management, incident documentation, and first aid advice for basic on-site patient management, general medical and clinical toxicology consultation for health care providers, and health and safety information to the study participants, customers, medical personnel, and others. Services are provided by telephone 24 hours a day, 365 days a year.

SafetyCall will also provide adverse event management and incident documentation for non-telephone based correspondence such as consumer email, customer service notifications, internet-based inquiries and written communications. These services include an initial professional assessment for health risk and triage. SafetyCall will respond to any inquiries it receives, including incidents involving either humans or animals consistent with standard of care practices. A lead toxicologist is available from 9:00am to 5:00pm Central Standard Time, Monday through Friday. An on-call toxicologist is available after hours.

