SafetyCall will also manage reporting of AEs to the FDA. In compliance with the Dietary Supplement and Nonprescription Drug Consumer Protection Act (Pub. L. 109-462, 120 Stat. 3469), any correspondence or verbal notification of a potential adverse event (AE) in association with a dietary supplement received by a manufacturer and/or its subsidiaries will be documented according to FDA mandated data collection guidelines and all records retained for a minimum of 6 years for potential review by the FDA. Those

adverse events meeting the FDA defined criteria for serious will be reported to the FDA within 15-business days using the FDA Form 3500A and its accompanying data elements.

Study Oversight

This study will be made available for monitoring, auditing, IRB review and regulatory inspection by providing direct access to study related source data.

Ethical and Regulatory Standard

This study will be conducted in conformance with the principles set forth in The Belmont Report: Ethical Principles and Guidelines for the Protection of Human Subjects of Research (US National Commission for the Protection of Human Subjects of Biomedical and Behavioral Research, April 18, 1979) and the Declaration of Helsinki.

This study is to be conducted in compliance with the IRB approved protocol and according to applicable federal, state, local and tribal laws including the following:

- US Code of Federal Regulations (CFR) governing clinical study conduct: Title 45 Part 46 – Protection of Human Subjects
- US Code of Federal Regulations relating to the Health Insurance Portability and Accountability Act of 1996: Title 45 Part 164 – Security and Privacy – Subpart E - ○ Subpart E—Privacy of Individually Identifiable Health Information
- State of California Health and Safety Code, Title 17, for research conducted in California

In addition, this study is to be conducted in compliance with applicable policies and procedures of the Advarra IRB, applicable institutional research policies and procedures, applicable institutional clinical policies and procedures, and applicable NIH policies and procedures.

IRB Review / Ethics / Informed Consent

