The study PI or the IRB may terminate or suspend this study at any time. If the study is prematurely terminated or suspended, participants will be instructed as to whether they should complete supplementation. Participants will be monitored and continue follow up for 2 weeks after they stop supplementation to ensure their safety and to collect any final data. All participants who have completed at least 50% of surveys at the time that the study is terminated or suspended will be provided with a discount code to purchase the Nella probiotic as compensation.

Informed Consent

Informed consent is a process that is initiated prior to the individual agreeing to participate in the study and continues throughout study participation. Operational details specific to the consenting process that occurs prior to any research evaluations/interventions are described in Section 6.0.

All participants will undergo virtual electronic informed consent after they are determined to qualify for the study. An electronic informed consent document will describe the nature, duration, purpose of the study, potential risks, alternatives and potential benefits, and all other IRB approved information. In addition, the experimental participant's bill of rights and the HIPAA research authorization form will be provided. Prospective research participants will be informed that they may withdraw from the study at any time and for any reason without prejudice. Prospective research participants will be afforded sufficient time to consider whether to participate in the research.

Virtual informed consent will be conducted through the app-based consent form at the participant's convenience. After reading the consent, participants will be able to contact study staff about any study related questions. Once the prospective participant expresses full understanding, virtual informed consent will be obtained through electronic signature from either the prospective participant before study participation. The method of obtaining and documenting the informed consent and the contents of the consent must comply with the ICH-GCP and all applicable regulatory requirements. A copy of the signed consent document will be available to the participant within the Chloe app. The signed consent must be maintained by the investigator and available for inspection by sponsor designated representatives, or regulatory authority at any time.

Privacy Authorization

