The informed consent process will include a privacy authorization compliant with 45CFR164.508(c) via the inclusion/incorporation of:

- all core elements specified in 508(c)(1) including the signature of the individual (or representative) and date of signature,
- all required statements specified in 508(c)(2)
- the plain language requirement as specified in 508(c)(3), and
- the provision to the participant (or representative) a copy of the signed authorization (508(c)(4)

State of California Human Experimentation Requirements

This research involves the collection of information via validated questionnaires and obtaining information from the medical record. Research activities do not encompass those that are requisite for a participant to be involved in a “medical experiment” as defined by California State Law 24174. The ‘California Experimental Subject’s Bill of Rights’ will be administered as part of the informed consent process; as part of that process participants will receive a copy of the ‘Bill of Rights’ marked with their signature.

Data Management

Study data will be stored in secure password-protected servers. Study staff will de-identify all data prior to data analysis. Data will be analyzed to compare the safety and efficacy of Veillonella vs placebo and between the two different doses of Veillonella. We will also use these data to better understand the type of benefits different subsets of participants tend to experience as well as the magnitude of the benefit in these subpopulations. These results will be used to create peer-reviewed publications, academic and industry presentations, file patents, and potentially develop new innovative microbiome products like probiotics. Participants will not be notified of any of these uses.

Confidentiality

All documents and electronic data will be stored on secure, password-protected computers. Participant confidentiality will be strictly held in trust by the investigators, study personnel, and sponsor. No identifiers will be used in any subsequent publication of these results.

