The publication or presentation of any study results shall comply with all applicable privacy laws, including, but not limited to, the Health Insurance Portability and Accountability Act of 1996. Neither the complete nor any part of the results of the study carried out under this protocol, nor any of the information provided by the sponsor for the purposes of performing the study, will be published or passed on to any third party without the written approval of the Study PI. Any investigator involved with this study is obligated to provide the sponsor with all data derived from the study.

Biostatistical Analysis Plan

Data Source

The source of the data is the results of the questionnaires filled out through the Chloe app as well as the optional fitness tracker data collected over the course of the study.

Analysis Objectives

The goals of this analysis are to identify whether there are statistically significant differences in effects between the placebo and Veillonella groups as well as between the high and low dose Veillonella groups. Furthermore, for any differences that are observed, we would like to understand whether there are any demographic or other participant characteristics that may be associated with benefits or side effects experienced by the participants.

Analysis Sets / Populations / Subgroups

The three groups compared in this study are high dose Veillonella, low dose Veillonella, and placebo.

In addition, we plan to separately analyze results by gender, age, baseline exercise habits, health history, previous probiotic experience, sleep habits, and other lifestyle factors.

For those participants who share fitness tracker data, the fitness tracker data shared through the Chloe app will be analyzed in conjunction with survey data separately from those who did not share fitness tracker data.

Endpoints

The primary endpoints analyzed in this study are:

- Change in reported physical fatigue
- Change in mental / emotional fatigue
- Change in MFI

The secondary endpoints analyzed in this study are:

- Change in reported sleep quality
- Change in frequency of reported physical activity
- Change in intensity of reported physical activity
- Change in reported exercise
- Change in recovery time
- Change in energy level

The exploratory endpoints analyzed in this study are:

- Changes in fitness tracker data
- Change in reported bowel movements
- Change in GSE
- Change in reported mood
- Change in reported digestive health

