- Change in reported general health
- Change in BMI, weight, or waist circumference

Handling of Missing Values

There will likely be missing values related to incomplete or missing surveys. Participants will only be included in the analysis if they completed at least 50% of weekly surveys during each time period: baseline, supplementation, and washout. Values will be binned longitudinally such that each participant included in the analysis has a data point associated with each bin. If there are multiple values associated with a participant in a bin, the mean of those values will be used for the analysis.

Statistical Procedures

The majority of primary and secondary endpoints for this study are questions on the survey which consist of rating scales (generally 1-5 or 1-9). Significant differences between groups for these endpoints will be assessed using an independent T test or Mann-Whitney U test depending on the observed

distribution of the data. For significant changes over time within the same group, a dependent T test will be used.

For differences between groups in terms of primary and secondary endpoints that measure a change in time (e.g. time to recovery in days or hours of sleep), an independent T test or Mann-Whitney U test will be used, depending on the observed distribution of the data. For significant changes over time within the same group, a dependent T test will be used.

To identify demographics associated with any particular response (benefit or side effects), we will use the demographic, health history, and lifestyle information collected in the surveys to build an unsupervised machine learning algorithm (e.g. Random Forest Classifier). If we can build one that effectively classifies the response (AUC > 0.7), we will identify the model's most important features. To confirm that these features are significantly associated with response, we will use an independent T test to assess significant differences between response and non-response.

For all other exploratory endpoints including the optional fitness tracker data, the data type and distribution of that data will determine the statistical analysis used.

Measures to Adjust for Confounders

For all data and endpoints, data can be normalized to the baseline collected values, and change in value at different time points can be compared using the statistical tests described above.

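### As worded, the 50% weekly-survey rule drops everyone who fully withdraws during dosing from the side-effect comparison, because no safety exception or safety set is stated

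*Combined protocol and SAP*

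**What the plan says.** The only inclusion rule in the Biostatistical Analysis Plan is under Handling of Missing Values: participants will "only be included in the analysis if they completed at least 50% of weekly surveys during each time period: baseline, supplementation, and washout". The sentences after it describe grouping values into time bins, so that each included participant has a value in every bin, and averaging where a bin holds several.

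Analysis Sets / Populations / Subgroups names the three treatment groups, a list of subgroups and a split by fitness-tracker sharing. It names no safety set.

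Side effects are nevertheless to be analysed. Data Management states: "Data will be analyzed to compare the safety and efficacy of Veillonella vs placebo and between the two different doses of Veillonella". Analysis Objectives asks, for any differences seen, about "participant characteristics that may be associated with benefits or side effects experienced by the participants". Statistical Procedures plans a classifier with side effects as one possible response.

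On collection, Monitoring/Reporting of AE/SAE says "AEs and SAEs will be detected using the weekly surveys". It also lets participants report by phone or email and engages an outside call service. That service must document "any correspondence or verbal notification of a potential adverse event (AE) in association with a dietary supplement" that reaches the manufacturer. Data Source, however, lists only the app questionnaires and the optional tracker data. On leaving, the protocol says: "Participants may withdraw from the study at any time and for any reason without prejudice. The withdrawal must be documented".

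**The concern.** A side-effect comparison should count the people who were exposed. This rule counts people by whether they were still answering surveys in washout, which is settled after dosing and may itself depend on side effects. Someone who leaves in the second week of capsules because of nausea, and says so, would be missing from that arm's numerator and denominator alike.

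Safety is part of the first stated objective, and the protocol describes this as the largest study of the strain's safety and efficacy. If affected and unaffected people leave at different rates, each arm's side-effect rate is distorted. If that pattern also differs by arm, the odds ratio between arms is distorted too.

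**Working it through.** The plan gives no withdrawal rate and no side-effect calculation, so there is no figure of its own to reproduce.

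**Step 1: what the rule requires.** Table 2 has one weekly survey at the end of each of eight weeks: baseline is Weeks 1–2 (2 surveys), supplementation Weeks 3–6 (4) and washout Weeks 7–8 (2). Half of each is 1 of 2, 2 of 4 and 1 of 2.

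**Step 2: who passes.** Take a participant who completes every survey up to a given week and then leaves for good.

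| Last survey completed | Baseline | Supplementation | Washout | Result |
|---|---|---|---|---|
| Week 2 (leaves in Week 3) | 2/2 | 0/4 | 0/2 | excluded |
| Week 3 | 2/2 | 1/4 | 0/2 | excluded |
| Week 4 | 2/2 | 2/4 | 0/2 | excluded |
| Week 5 | 2/2 | 3/4 | 0/2 | excluded |
| Week 6 | 2/2 | 4/4 | 0/2 | excluded |
| Week 7 | 2/2 | 4/4 | 1/2 | included |
| Week 8 | 2/2 | 4/4 | 2/2 | included |

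Every full withdrawal during dosing fails on washout. The most complete excluded participant has 2 + 4 = 6 of 8 surveys (75%) and all four on-treatment surveys. This step needs no assumption.

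**Step 3: what it could do to the comparison (illustration only).** Let p be the true side-effect rate, a the share of affected people who leave, and u the share of unaffected people who leave. The rate among those analysed is

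p(1 − a) / [p(1 − a) + (1 − p)(1 − u)].

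Inputs:
- p = 10% on Veillonella, the lower bound given under Risk/Safety Information for the very common effects.
- p = 5% on placebo, assumed; that section lists no known risks for placebo.
- u = 10% in both arms, assumed.
- a = 10% or 30%, assumed.

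Arm results:
- Veillonella, a = 10%: 0.09 / (0.09 + 0.81) = 10.0%
- Veillonella, a = 30%: 0.07 / (0.07 + 0.81) = 7.95%
- Placebo, a = 10%: 0.045 / (0.045 + 0.855) = 5.0%
- Placebo, a = 30%: 0.035 / (0.035 + 0.855) = 3.93%

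The true odds ratio is (0.10/0.90) / (0.05/0.95) = 2.11. With equal u, the analysed odds ratio is 2.11 times (1 − a) on Veillonella over (1 − a) on placebo.

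| Affected who leave (Veillonella / placebo) | Difference, points | Error against 5.0 | Odds ratio |
|---|---|---|---|
| 10% / 10% | 5.0 | 0 | 2.11 |
| 30% / 30% | 4.0 | −1.0 | 2.11 |
| 30% / 10% | 3.0 | −2.0 | 1.64 |
| 10% / 30% | 6.1 | +1.1 | 2.71 |

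These are scenarios, not limits. For example, if half of affected people leave in both arms on top of the 10% general loss, the general loss cancels. The rates become 0.05/0.95 = 5.3% and 0.025/0.975 = 2.6%, a difference of 2.7 points (error −2.3).

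**The case against.** The strongest reply is that the rule was never meant for safety. It sits under missing values, next to text about bins and means that suits repeated ratings and not event counts. No adverse event is listed as an endpoint and no test of event rates is specified. The promise to compare safety is made in Data Management, outside the analysis plan. This makes an efficacy-only intent plausible, and the documents do not say outright that the rule governs adverse events. But the rule refers to the analysis without qualification, the same plan takes side effects as a response, and nothing exempts them. An analyst following the text has no other set to use.

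Three stronger readings are tempting and are not supported:

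- **That safety reports are lost.** They are not. Events that are mentioned must be documented, serious ones go to the FDA, and phone, email and the call service stay open. The gap is in the comparison between arms.
- **That everyone who stops because of a side effect is excluded.** The weekly survey asks whether the product was stopped for side effects, so it expects such people to keep answering. If they do, they can meet the rule. Only full withdrawal triggers the exclusion.
- **That people who leave are never asked about symptoms.** The surveys they completed included a symptom question. The protocol describes no exit question, but a requirement to document withdrawal does not rule one out. Consent pages are not available, so this rests on silence in the protocol.

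**Conclusion.** The concern holds as a defect of wording with a definite consequence. Read as written, the rule removes every participant who fully withdraws from the start of Week 3 until the Week 7 survey from the side-effect comparison, whatever they have already reported. That part is arithmetic from Table 2. It rests on one reading, that the unqualified rule covers side effects; this is the natural reading, though possibly not the intended one.

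How many people this affects is unknown, since no withdrawal rate is given. A reader might infer that the rule hides harm. The documents do not support that: the illustration includes no error, an understated difference (3.0 against 5.0 points) and an overstated one (6.1), and all its inputs except the 10% are assumed. The effects expected on Veillonella are also described as mild or transient, so few people may leave because of them. The plan should be changed because the correction is cheap and the rule gives no benefit for safety data. Confidence is medium.

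**What to change.** 1. In Handling of Missing Values, limit the 50% rule to the efficacy endpoints.
2. In the same place, or under Analysis Sets, state that side effects are reported by randomized arm for all randomized participants who started supplementation. No capsule-start record is described, so where the start is unknown, count everyone not known to have left before Week 3 or to have taken no capsule. Show withdrawals by arm beside the side-effect counts.
3. In Data Source, add adverse-event reports received by phone, email and the call service. Without this, reports from people who have left would still fall outside the stated source.

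The cost is a few sentences and, because the analysis plan is part of the protocol, an amendment approved by the IRB. Some people who never took a capsule may be counted, which dilutes the rates by an amount that cannot be estimated from the documents. Safety data on people who leave silently will remain incomplete.

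Optional and secondary: at a notified withdrawal, record the reason, the date of the last capsule and current symptoms. The protocol already sets a fuller standard if the whole study is stopped early: "Participants will be monitored and continue follow up for 2 weeks after they stop supplementation to ensure their safety and to collect any final data". Steps 1 to 3 stand without this addition.

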Once participants are invited to the study, they will be sent an email with a link to the Chloe application, which they will download to their mobile device. Chloe will lead them through a detailed description of the study and the informed consent process. At this point, they will also consent to sharing their fitness tracker data, as an option, if they have one. The fitness tracker data will be used to answer sleep questions and other fitness tracker data will be stored for analysis by the FitBiomics team. Once informed consent is obtained, participants will fill out a baseline health and lifestyle survey, where they will also share their mailing address. Once this survey is completed, the participant will be randomized to a high dose Veillonella (15 billion cfu), low dose Veillonella (7.5 billion cfu), or placebo in a 4:4:2 ratio respectively. These capsules will be mailed to the participant during the 2 week baseline period.

Completion of the initial baseline health and habit survey initiates the 2 week baseline period. During this period, participants will fill out daily surveys on sleep, energy, and bowel movements and weekly surveys on other benefits and adverse events (AEs) they have noticed (more details on all surveys can be found in Tables 1 and 2). On the final day of the two week baseline, they will also fill out the Multidimensional Fatigue Inventory (MFI) and General Self-Efficacy (GSE) questionnaires. At this point, participants will begin supplementation. Participants will supplement with one capsule daily for 4 weeks. During the supplementation phase, participants will fill out the same daily and weekly surveys. On the final day of the supplementation period, participants will also fill out the Multidimensional Fatigue Inventory and General Self-Efficacy questionnaires. After supplementation, there will be a two week washout period to monitor patients and to understand the lasting effect of any benefits they experienced. During the washout period, participants will again fill out the same daily and weekly surveys. On the final day of the washout period, there will be two additional surveys: one with some additional questions on changes observed throughout the study and one of open ended questions on the whole study experience.

Figure 1. Study Procedures

[figure not shown]

Table 1. Survey Details

| Survey Name | Survey Details | Number of Questions | Estimated Time to complete | Number of Times Used | Total survey time |

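### The 50% completion rule and the binning rule together let the two weekly fatigue primary endpoints be averaged over different treatment weeks in different participants

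*Combined protocol and SAP*

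**What the plan says.** Under Handling of Missing Values in the Biostatistical Analysis Plan, a participant is analysed only if they "completed at least 50% of weekly surveys during each time period: baseline, supplementation, and washout". The next sentences read: "Values will be binned longitudinally such that each participant included in the analysis has a data point associated with each bin", and "If there are multiple values associated with a participant in a bin, the mean of those values will be used for the analysis". No number, width or edges of bins are given.

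The period lengths come from the study procedures: "Completion of the initial baseline health and habit survey initiates the 2 week baseline period"; "Participants will supplement with one capsule daily for 4 weeks"; "After supplementation, there will be a two week washout period". Tables 1 and 2 schedule 8 weekly surveys, one per study week, which agrees with 2 + 4 + 2. Supplementation covers Weeks 3-6.

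Under Endpoints, the first primary endpoint is "Change in reported physical fatigue". The second is the corresponding change in mental/emotional fatigue, and the third is change in MFI. No time point is attached to the first two. The section on confounders allows changes at various time points to be compared and names none. The MFI is collected only at the end of Weeks 2 and 6.

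**The concern.** At first sight the plan merely omits a bin width. The difficulty goes further, because the obvious widths do not fit the stated rules. Two of four surveys are enough for inclusion, but every included participant needs a value in every bin. A participant who answered only Weeks 3 and 4, or only Weeks 5 and 6, has an empty fortnightly bin. Writing a weekly or fortnightly width into the SAP would therefore not cure the problem by itself.

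What is at stake is the definition of two primary endpoints. If one wide bin is used, a participant's on-treatment value is a mean over the weeks they happened to answer, and values from different weeks are tested as one quantity. If finer bins are used, either they are chosen once the missing-data pattern is known, or some participants who pass the 50% rule drop out. None of these is a prespecified primary endpoint.

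**Working it through.** The plan states no effect size, SD, power or calculated sample size, so there is no design figure to reproduce. I take the two reported-fatigue endpoints to come from the weekly survey: Table 1 describes it as collecting fatigue ratings, and the 50% rule refers to it.

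**1. Admissible patterns in Weeks 3-6.** At least 2 of 4 surveys gives C(4,2) + C(4,3) + C(4,4) = 6 + 4 + 1 = 11.

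**2. Which bins are always filled.** Weeks 3-6 can be cut into consecutive, non-overlapping bins in 2³ = 8 ways.

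| Cut of Weeks 3-6 | Patterns with an empty bin |
|---|---|
| One bin, 3-6 | 0 of 11 |
| 3-4, 5-6 | 2 of 11 |
| 3-5, 6 | 4 of 11 |
| 3, 4-6 | 4 of 11 |
| Each of the three three-bin cuts | 8 of 11 |
| Four weekly bins | 10 of 11 |

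Only the four-week bin satisfies both rules for every pattern. These are counts of patterns, not of people.

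**3. How many people are affected.** Assume each survey is missed independently with probability q. Then P(included) = (1-q)⁴ + 4q(1-q)³ + 6q²(1-q)². The share with fewer than four surveys is 1 - (1-q)⁴/P(included). The share with an empty fortnight is 2p, where p = q²(1-q)²/P(included). Two randomly chosen included participants share no week with probability 6p², because each two-week pattern has one complement.

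| q | P(included) | Fewer than 4 surveys | Empty fortnight | Pair shares no week |
|---|---|---|---|---|
| 5% | 0.9995 | 19% | 0.5% | 0.003% |
| 10% | 0.9963 | 34% | 1.6% | 0.04% |
| 20% | 0.9728 | 58% | 5.3% | 0.4% |

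The chance that fortnightly bins happen to be filled for all n included participants is (1 - 2p)ⁿ. At q = 5% this is 0.64 for n = 100 and 0.01 for n = 1,000. The latter assumes that all of the estimated 1,000 invitees enrol and are analysed.

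**4. Change score against baseline adjustment.** Assume compound symmetry with unit variance, correlation ρ and complete data. The four-week mean has variance (1+3ρ)/4, the two-week baseline mean (1+ρ)/2, and their covariance is ρ.

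- Change score: (1+3ρ)/4 + (1+ρ)/2 - 2ρ = 0.75(1-ρ). This is 0.450 at ρ = 0.4 and 0.150 at ρ = 0.8.
- Baseline as covariate: (1+3ρ)/4 - ρ²/[(1+ρ)/2]. This is 0.550 - 0.229 = 0.321 at ρ = 0.4, and 0.850 - 0.711 = 0.139 at ρ = 0.8.
- Reduction: 1 - 0.321/0.450 = 29%, and 1 - 0.139/0.150 = 7%.

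**5. Choice of window.** With baseline adjustment, the Weeks 5-6 mean has variance (1+ρ)/2 - ρ²/[(1+ρ)/2], which is 0.471 at ρ = 0.4 and 0.189 at ρ = 0.8.

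- Immediate onset: Weeks 5-6 needs 0.471/0.321 = 1.47 or 0.189/0.139 = 1.36 times the participants of the four-week mean. With change scores the factor is (1-ρ)/[0.75(1-ρ)] = 1.33.
- Linear build-up of 25/50/75/100% (assumption): the mean effects are 62.5% (four weeks) and 87.5% (Weeks 5-6) of the Week 6 effect. The four-week mean then needs (0.875/0.625)² = 1.96 times the inverse of those factors: 1.34 to 1.44 with baseline adjustment, 1.47 with change scores.

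**The case against.** The plan never states a four-week bin. A reader might infer that the rules force one, but that holds only for fixed, non-overlapping bins inside each period. Overlapping windows (Weeks 3-5 and 4-6) are always filled, and so are some bins that cross period borders, such as Weeks 1-3, which would mix baseline with treatment. The 50% rule is also worded as a necessary condition, so the bin sentence could be a further exclusion. On that reading fortnightly bins are workable, and in the illustration they would remove 0.5-5.3% of those who pass the 50% rule. This stands, but the unstated bin edges then decide who is analysed, and weekly bins would remove 19-58%.

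A reader might also infer that early weeks dilute the treatment effect. The documents give no onset time. With immediate onset there is no dilution, and the four-week mean is the more precise choice. For the same reason the documents do not require Weeks 5-6 to be primary. An average over the whole treatment period is a legitimate endpoint and need not match the MFI, which is a separate instrument.

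Finally, a reader might infer bias from early stopping that differs by arm. Inclusion also needs at least one of the two washout surveys, so anyone who stops answering for good is already excluded. A participant with Weeks 3-4 only must skip Weeks 5-6 and then return. Excluding dropouts is a separate issue from binning.

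Fully disjoint measurement weeks would be rare under the assumed missingness, as the last column of the table shows.

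**Conclusion.** The concern holds in a limited form. For fixed, non-overlapping, within-period bins, a single Weeks 3-6 bin is the only one filled for every participant the 50% rule can admit. Any finer bin must be chosen after seeing the missing data or must exclude people who meet that rule. Two of the three primary endpoints then rest on means over the weeks each participant answered. On independent missingness of 5-20% per survey, about 19-58% of included participants would be averaged over fewer than four weeks, mostly with partial overlap. The MFI endpoint is not affected.

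The enumeration needs no assumption beyond the type of bin. The percentages of participants and the 7-29% variance reduction are illustrations on the stated assumptions. Loss of effect from early weeks and bias from differential stopping are not established. The choice of window is a trade-off: with baseline adjustment, the wrong choice costs roughly 34-47% more participants in either direction, depending on an onset profile the plan does not give.

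**What to change.** For the two weekly fatigue endpoints, replace binning and tests on available-week means with a repeated-measures mixed model on the weekly ratings from Weeks 3-6. Include arm, week as a categorical factor, arm-by-week interaction, and the mean of the Weeks 1-2 ratings as a covariate. Every arm is then estimated at the same weeks, and no participant needs a value in every bin. The model assumes that missing ratings are missing at random given the observed ones, and the SAP should say so.

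Name one primary treatment window before the data are examined. One option is the arm difference averaged over Weeks 3-6, with the Weeks 5-6 contrast from the same model as secondary. The reverse is reasonable if the sponsor expects a gradual onset and states why. State separately whether the 50% rule still applies to these endpoints.

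The surveys are already scheduled, so no data collection changes. The cost is SAP wording, somewhat more modelling work, and a statistics library beyond those listed under Programming Plans.
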